7. PLANNED ANALYSIS

The format of the listings and tables will follow the standards defined in the BI standards with the exception of those generated for PK-calculations (6).

The individual values of all subjects will be listed. Listings will be sorted by treatment sequence, subject number and visit (if visit is applicable in the respective listing). AE listings will be sorted by assigned treatment (see [Section 7.8.1](#) below for details). The listings will be contained in Appendix 16.2 (SDL) of the CTR.

The following standard descriptive statistical parameters will be displayed in summary tables of continuous variables:

N	number of non-missing observations
Mean	arithmetic mean
SD	standard deviation
Min	minimum
Median	median
Max	maximum

For plasma concentrations as well as for all PK parameters the following descriptive statistics will additionally be calculated:

CV	arithmetic coefficient of variation
gMean	geometric mean
gCV	geometric coefficient of variation

For PK parameters the following descriptive statistics will additionally be calculated:

P10	10 th percentile
Q1	1 st quartile
Q3	3 rd quartile
P90	90 th percentile

The data format for descriptive statistics of plasma concentrations will be identical with the data format of the respective concentrations. The descriptive statistics of PK parameters will be calculated using the individual values with the number of decimal places as provided by the evaluation program. Then the individual values as well as the descriptive statistics will be reported with three significant digits in the CTR.

Tabulations of frequencies for categorical data will include all possible categories and will display the number of observations in a category as well as the percentage (%) relative to the respective treatment group. Percentages will be rounded to one decimal place. The category missing will be displayed if and only if there actually are missing values. Percentages will be based on all subjects in the respective subject set whether they have non-missing values or not.

7.1 DEMOGRAPHIC AND OTHER BASELINE CHARACTERISTICS

Only descriptive statistics are planned for this section of the report.

7.2 CONCOMITANT DISEASES AND MEDICATION

Concomitant diseases will be coded according to the most recent version of MedDRA. Concomitant medication will be coded according to the most recent version of the World Health Organisation – Drug Dictionary.

Only descriptive statistics are planned for this section of the CTR.

7.3 TREATMENT COMPLIANCE

Treatment compliance will not be analyzed as a specific endpoint. Any deviations from complete intake will be addressed in the Report Planning Meeting (cf. [Section 6.2](#)) and described in the CTR.

7.4 PRIMARY ENDPOINT

CTP Section 7.3.1: “*The derivation of the primary endpoint PSS sum intensity score per time point is outlined in Section 5.6.3. The maximum CfB is defined as the maximum of the differences of the PSS sum intensity score measured at each time point after the CCK-4 challenge minus the PSS sum intensity score measured at baseline.*”

7.4.1 Primary analysis of the primary endpoint

The primary endpoint will be analyzed based on the PDS.

Descriptive statistics and boxplots of the primary endpoint by treatment will be provided.

As main analysis, the following model will be applied:

Statistical model

CTP Section 7.3.1: “*The statistical model used for the investigation of the primary endpoint PSS sum intensity score will be a mixed effects model given by*

$$y_{imj} = \mu + \pi_m + \tau_j + \gamma b_{im} + \gamma' b'_i + s_i + e_{imj},$$

where

y_{imj}	Maximum CfB (absolute change from period baseline) in PSS sum intensity score for the ith subject and the mth period, receiving randomised treatment j,
μ	overall intercept,
π_m	mth period effect, $m = 1, 2$,
τ_j	jth treatment effect, $j = 1, 2$,
b_{im}	baseline value for subject i in period m (period baseline),
γ	associated covariate effect of period baseline,
b'_i	the subject baseline value (mean of the 2 period baselines) for subject i,
γ'	associated covariate effect of subject baseline,
s_i	the random effect of subject i,
e_{imj}	the random error associated with subject i who received treatment j in period m.

The last value before administration of the CCK-4 challenge in each period is considered as the corresponding period baseline measurement. The PSS sum intensity score mean value of the two period baseline values is considered as the subject baseline.

The treatment comparison will be the difference between active treatment and placebo. Adjusted means (Least Squares Means) as well as 2-sided 90% CIs will be calculated. Additionally, the difference in adjusted means relative to placebo will be provided. To support this analysis, listings and graphical displays may be generated if appropriate.

As a sensitivity analysis, the same statistical model as stated above will be repeated for the primary endpoint but with all sources of variation considered as fixed effects.”

For the random ‘subject’ effect in the above model a Variance Components (VC) covariance structure will be used; in case of convergence problems refer to Additional [Section 9.2](#). The SAS procedure MIXED will be used involving the restricted maximum likelihood estimation and the Kenward-Roger approximation for denominator degrees of freedom. This approach is described in Kenward and Roger ([8](#)).

Programming details are provided in [Section 9.1.1](#).

7.4.2 Sensitivity analysis, subgroup analysis, exploratory analysis of the primary endpoints

CTP Section 7.3.1: *As a sensitivity analysis, the same statistical model as stated above will be repeated for the primary endpoint but with all sources of variation considered as fixed effects.*

7.5 SECONDARY ENDPOINTS

Not applicable.

7.6.1 Safety parameters

Safety and tolerability will be analysed as described in [Section 7.8](#) of this TSAP.

7.7 EXTENT OF EXPOSURE

Treatment exposure will be listed by means of the date and time of drug administration.

7.8 SAFETY ANALYSIS

All safety analyses will be performed on the TS.

7.8.1 Adverse Events

AEs will be coded with the most recent version of MedDRA.

The analyses of AEs will be descriptive in nature. All analyses of AEs will be based on the number of subjects with AEs and not on the number of AEs.

For analysis, multiple AE occurrence data on the eCRF will be collapsed into one event provided that all of the following applies:

- All AE attributes are identical (lower level term, intensity, action taken, therapy required, seriousness, reason for seriousness, relationship, outcome, AESI)
- The occurrences were time-overlapping or time-adjacent (time-adjacency of two occurrences is given if the second occurrence started at most 1 hour after the first occurrence ended)

The analysis of AEs will be based on the concept of treatment emergent AEs. That means that all AEs will be assigned to screening or on-treatment phases as defined in [Section 6.1](#). AEs will be analysed based on actual treatments, as defined in [Table 6.1: 1](#).

An overall summary of AEs will be presented. This overall summary will comprise summary statistics for the class of other significant AEs according to ICH E3 ([7](#)) and for the class of AESIs.

CTP, Section 5.2.6.1.6: “*The following are considered as AESIs:*

- *Hepatic injury*
A hepatic injury is defined by the following alterations of hepatic laboratory parameters:
 - *An elevation of AST (aspartate transaminase) and/or ALT (alanine transaminase) ≥ 3 -fold ULN combined with an elevation of total bilirubin ≥ 2 -fold ULN measured in the same blood sample, or*
 - *Aminotransferase (ALT, and/or AST) elevations ≥ 10 fold ULN”*

The investigator had to classify on the eCRF whether an observed AE was an AESI or not.

According to ICH E3 ([7](#)), AEs classified as "other significant" need to be reported and will include those non-serious and non-significant AEs

- (i) which are marked haematological or other lab abnormalities, or
- (ii) which were reported with "action taken = discontinuation" or "action taken = reduced", or
- (iii) which lead to significant concomitant therapy as identified by the Clinical Monitor/Investigator at a Medical Quality Review Meeting.

The frequency of subjects with AEs will be summarised by treatment, primary SOC and preferred term. AEs which were considered by the investigator to be drug related will be summarised separately. Separate tables will also be provided for subjects with SAEs, subjects with AESIs and subjects with other significant AEs (according to ICH E3 ([7](#))). The frequency of subjects with AEs and the frequency of subjects with AEs considered by the investigator to be drug related will also be summarised by maximum intensity, primary SOC and preferred term.

The SOCs and preferred terms within SOCs will be sorted by descending frequency over all treatment groups.

For disclosure of AE data on ClinicalTrials.gov, the frequency of subjects with non-serious AEs occurring with an incidence of greater than 5 % (in preferred terms) will be summarised by treatment, primary SOC and preferred term. The frequency of subjects with SAEs will also be summarised.

For disclosure of AE data in the EudraCT register, the frequency of AEs, the frequency of non-serious AEs with an incidence of greater than 5 % (in preferred terms) and the frequency of SAEs will be summarized.

For support of lay summaries, the frequency of subjects with drug-related SAEs will be summarized by treatment, primary SOC and preferred term.

If the subject reports headaches during the treatment period further information about the duration of headache, headache severity (NRS), location, characteristics, and signs and symptoms were recorded. The information will be summarized with descriptive statistics.

7.8.2 **Laboratory data**

The analyses of laboratory data will be descriptive in nature and will be based on BI standards.

Analyses will be based on normalised values, which means transforming to a standard unit and a standard reference range. The original values will be analysed if the transformation into standard unit is not possible for a parameter.

Descriptive statistics of laboratory values over time and for the difference from baseline (see [Section 6.7](#)) will be provided. Frequency tables of changes between baseline and last value on treatment with respect to the reference range will be presented.

Possibly clinically significant abnormal laboratory values are only those identified either in the Investigator's comments or at the Report Planning Meeting at the latest. It is the Investigator's responsibility to decide whether a lab value is clinically significant abnormal or not. Standard or project-specific rules for flagging clinically significant values in an automated manner will not be applied in this study.

Clinically relevant findings in laboratory data will be reported as baseline conditions (prior to first administration of study treatment) or as AEs (after first administration of study treatment) if judged clinically relevant by the investigator, and will be analyzed as such.

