1.4.2.1.1 Risks derived from observations in non-clinical studies

1.4.2.1.2 Mode of action and nature of the target

1.4.2.1.3 Relevance of animal models

1.4.2.1.4 Risk minimization (safety precautions and stopping rules)

The following safety measures will be applied in this study in order to minimize the risk for healthy volunteers:

- For safety reasons, each treatment period will be divided into 4 cohorts of 5 subjects. Each drug administration will be separated by at least 10 minutes and the dosing of the cohorts will be separated by at least 2 days. Adequate continuous safety monitoring (see below) will be performed before the subsequent cohort is dosed.
- An extensive safety laboratory will be performed with special focus on full blood exam, including CRP and ESR to monitor for potential perivascular/mesenteric inflammation (see [Flow Chart](#))
- Adequate safety monitoring will be performed (e.g. vital signs (including blood pressure, pulse rate, respiratory rate), ECGs, safety laboratory tests including hormone parameters, visual analogue scales, suicidality, and assessment of adverse events)
- Subjects will be hospitalised throughout the study from Day -1 to Day 9 of each period and will be discharged only after a formal assessment and confirmation of fitness by an investigator or qualified designee. During the in-house stay, the subjects will be under medical observation and thoroughly monitored for adverse events, which may be reported in an expedited manner if they match the criteria for expedited reporting
- As reproductive toxicity studies have not yet been conducted, only male subjects will be enrolled in this study

Proprietary confidential information © 2019 Boehringer Ingelheim International GmbH or one or more of its affiliated companies

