3.3.4.1 Discontinuation of trial treatment

An individual subject will discontinue trial treatment if:

1. The subject wants to discontinue trial treatment, without the need to justify the decision
2. The subject has repeatedly shown to be non-compliant with important trial procedures and, in the opinion of both, the investigator and sponsor representative, is not willing or able to adhere to the trial requirements in the future
3. The subject needs to take concomitant medication that interferes with the investigational medicinal product or other trial treatment
4. The subject can no longer receive trial treatment for medical reasons (such as surgery, adverse events [AEs], or diseases)
5. An AE or clinically significant laboratory change or abnormality occurred that the investigator judges to warrant discontinuation of treatment. This may include cases of sustained symptomatic hypotension (BP <90/50 mmHg) or hypertension (BP >180/100 mmHg) or of clinically relevant changes in ECG requiring intervention as well as unexplained liver enzyme elevations at any time during the trial

Proprietary confidential information © 2019 Boehringer Ingelheim International GmbH or one or more of its affiliated companies

6. The subject has an elevation of AST and/or ALT ≥ 3 -fold ULN and an elevation of total bilirubin ≥ 2 -fold ULN (measured in the same blood sample) and/or needs to be followed up according to the DILI checklist provided in the ISF
7. The subject shows a raised CRP level of >3.00 mg/dL or an ESR of ≥ 20 millimeters/hour if these results are confirmed by a second sample.

In addition to these criteria, the investigator may discontinue subjects at any time based on his or her clinical judgment.

Even if the trial treatment is discontinued, the subject remains in the trial and, given his agreement, will undergo the procedures for early treatment discontinuation and follow up as outlined in the [Flow Chart](#) and [Section 6.2.3](#).

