Previous and concomitant therapies will be presented per treatment group without consideration of time intervals and treatment periods.

Laboratory data will be compared to their reference ranges. Values outside the reference range as well as values defined as possibly clinically significant will be highlighted in the listings. Additionally, differences from baseline will be evaluated.

Vital signs or other safety-relevant data will be assessed with regard to possible on-treatment changes from baseline.

Relevant ECG findings will be reported as AEs.

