6.7 BASELINE, TIME WINDOWS AND CALCULATED VISITS

A separate baseline is defined for each study treatment. The baseline is the last available value before administration of the CCK-4 challenge in the respective treatment period. E.g. for PSS sum intensity score baseline is the value measured 15 minutes before administration of the CCK-4 challenge within the respective treatment period.

In addition, for vital signs displays where PTM -2:00 are considered as baseline will be provided.

Time windows are defined in Section 6.1 of the CTP. Adherence to time windows will be checked at the Report Planning Meeting.

Unscheduled measurements of laboratory data or vital signs data will be assumed to be repeat measurements of the most recent scheduled measurement (e.g. for follow-up or confirmation of a particular value). Therefore, unscheduled measurements will be assigned to the planned time point of the previous scheduled measurement.

Descriptive statistics of laboratory data will be calculated by planned time point based on the worst value of the subject at that planned time point (or assigned to that planned time point). For vital signs, descriptive statistics will be calculated by planned time point based on the last value of the subject at that planned time point (or assigned to that planned time point).

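### SAP 7.8.2 builds its only laboratory shift table on the last on-treatment value, so a CRP, ESR or liver-enzyme rise that has resolved by then shows as no shift

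*SAP*

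**What the plan says.** **Laboratory displays.** SAP 7.8.2 plans two kinds of summary. The categorical one is: "Frequency tables of changes between baseline and last value on treatment with respect to the reference range will be presented". The continuous one is: "Descriptive statistics of laboratory values over time and for the difference from baseline". For the continuous summaries, SAP 6.7 adds: "Descriptive statistics of laboratory data will be calculated by planned time point based on the worst value of the subject at that planned time point". Unscheduled samples are assigned to the preceding scheduled time point. SAP section 7 lists minimum and maximum among the standard statistics. Protocol 7.3.4 adds: "Values outside the reference range as well as values defined as possibly clinically significant will be highlighted in the listings".

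**Flags and adverse events.** SAP 7.8.2 also states: "Standard or project-specific rules for flagging clinically significant values in an automated manner will not be applied in this study". A laboratory finding becomes an AE only when the investigator judges it clinically relevant. SAP 7.8.1 gives separate tables for AESIs, of which hepatic injury is the only one, and for other significant AEs. The latter include marked laboratory abnormalities and AEs that led to discontinuation.

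**Why CRP and ESR are measured.** Protocol 1.4.2.1.4 specifies an extended safety laboratory, "including CRP and ESR to monitor for potential perivascular/mesenteric inflammation". Protocol 3.3.4.1 item 7 then sets a discontinuation limit, which needs confirmation in a repeat sample: "The subject shows a raised CRP level of >3.00 mg/dL or an ESR of ≥ 20 millimeters/hour if these results are confirmed by a second" (last word omitted). Item 6 sets a paired AST/ALT and bilirubin limit.

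**The concern.** After a single dose, the last sample of a period is the one furthest from exposure. A reference-range table built on it describes whether subjects ended the period in range, not whether they left the range after dosing. For a drug given once, the second question is the one a safety reader will bring to the table.

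The choice matters more here because the protocol names an inflammatory risk, picks two markers for it and attaches numeric limits to them. Protocol 3.3.3 excludes subjects with CRP above the upper limit of normal, ESR of 15 mm/h or more, or raised liver parameters. Subjects therefore start close to normal, and a table of post-dose excursions would be easy to read. As planned, the shift table could show no CRP or ESR shifts on active treatment although subjects had transient excursions, and no other table would give the number of such subjects by treatment.

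**Working it through.** No power or error-rate figure is involved. The check is of timing, of the conditions for a hidden rise, and of what each display would show.

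**1. Earliest possible last value.** The Flow Chart puts the Day 9 discharge at 192:00 h, and its footnote 11 includes safety laboratory. Protocol 6.2.2 defines each treatment period as Days 1 to 9. So 192 / 24 = 8.0 days after dosing for a subject who completes the period.

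**2. Later candidates.** SAP Table 6.1: 1 gives an on-treatment end only for AEs. SAP 6.1 leaves technical detail for laboratory data to the ADS Plan. Protocol 7.3.4 ends the treatment assignment at the end of the residual effect period, whose length is not visible in this copy. If later samples count:

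- Period 1, admission sample of period 2 (18 h before dose 2, doses at least 17 days apart): 17 − 18/24 = 16.25 days or more.
- Period 2, end-of-trial (EOT) sample on Day 35 to 40, day origin not stated. Counted from the first dose with w days between doses, the interval is (35 to 40) − (1 + w):

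| Assumption | Days after dose 2 |
|---|---|
| w = 17 | 17 to 22 |
| w = 20 | 14 to 19 |
| w = 24 | 10 to 15 |
| counted from period 2 Day 1: (35 to 40) − 1 | 34 to 39 |

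Only the 8 days is fixed by the documents.

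**3. When a rise is hidden.** The value must be back in range by the last sample. Assume first-order decline from a peak of f times the upper limit of normal (ULN). The value is in range t days after the peak if its half-life is at most t / log2(f). The table takes the last sample as Day 9 and peaks at 24 h (t = 7) or 96 h (t = 4). Laboratory samples at those times look likely, but the Flow Chart columns are broken in this copy.

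| Peak | f | log2(f) | Longest half-life, peak at 24 h | Longest half-life, peak at 96 h |
|---|---|---|---|---|
| ALT/AST 3 × ULN | 3 | 1.58 | 4.4 days | 2.5 days |
| ALT/AST 10 × ULN | 10 | 3.32 | 2.1 days | 1.2 days |
| CRP 3.00 mg/dL, assumed ULN 1.0 | 3 | 1.58 | 4.4 days | 2.5 days |
| CRP 3.00 mg/dL, assumed ULN 0.5 | 6 | 2.58 | 2.7 days | 1.6 days (1.55) |
| ESR 20 mm/h, assumed ULN 15 | 1.33 | 0.42 | 16.9 days | 9.6 days |

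The CRP upper limits are assumptions, and 15 mm/h is the exclusion limit used as a stand-in for the ESR upper limit. Rises that decline more slowly than this still appear as a shift. Higher peaks need a faster decline to be hidden.

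**4. One subject traced through the displays.** Baseline is in range, CRP is above 3.00 mg/dL on an early sample and on its repeat, and the value is normal at the last sample.

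| Display | What it shows |
|---|---|
| Shift table (SAP 7.8.2) | Normal to normal |
| Statistics by time point (SAP 6.7, 7) | The worst value enters; it is the maximum if no one is higher; no count of subjects |
| Listing (protocol 7.3.4) | Value highlighted; no frequency by treatment |
| AESI table | Nothing; hepatic injury only |
| AE and other significant AE tables | Counted only if the investigator reports it as an AE |
| Count against the item 7 limits | Not planned in the available text |

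For a liver rise the AESI row changes: a rise meeting the hepatic-injury definition is counted there. A smaller transient enzyme rise follows the same path as CRP.

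**5. Size.** With 20 subjects per treatment, each hidden subject is 1/20 = 5 percentage points. The documents give no frequency or time course for such rises, so no expected number can be computed.

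**The case against.** The best defence is that the shift table is one display among several. Worst values by time point, with minimum and maximum, would expose an extreme CRP, and highlighted listings of about 20 subjects can be read by eye. The hepatic limits already have a table. The discontinuation rules work on values as they arise, not on the table. The trial is descriptive and no decision rule uses the shift table. All of this stands, and it limits the point to reporting. What it does not supply is a number of affected subjects by treatment for CRP and ESR: a maximum shows one subject, a listing shows no frequency, and the AE route depends on investigator judgement.

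A reader might also infer that a subject discontinued on a marker would necessarily show as no shift. The documents do not support that. Protocol 3.3.4 calls for a full end-of-trial examination at discontinuation, if possible, and this includes safety laboratory, so the last value may still be abnormal. It may also be normal: protocol 6.2.3 has relevant abnormal values followed until acceptable, and the SAP does not say whether those retests become the last value.

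A reader might see a contradiction between SAP 6.7 (worst value) and 7.8.2 (last value). There is none. The first chooses among repeats within a time point; the second chooses which time point enters the change table.

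**Conclusion.** The point holds as a limited weakness of display. In a completed period the shift table looks no earlier than 8 days after a single dose, and it records as no shift any CRP, ESR or liver-enzyme excursion that has resolved by then. For CRP and ESR, no other table in the available text counts the subjects concerned or those reaching the item 7 limits.

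Three stronger readings go too far:

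- That such events vanish from the report. They remain in the time-point statistics and listings, and in AE tables where judged relevant.
- That the liver limits go uncounted. The paired criterion in item 6 is part of the hepatic-injury AESI definition and has its own table, although AESI status is classified by the investigator.
- That the last value lies 8 to 22 days after dosing. The upper figure needs EOT days counted from the first dose and exactly 17 days between doses.

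The conclusion rests on the SAP text as available. The ADS Plan and the sponsor's laboratory standards are not in hand and could contain further displays. It also takes the Day 9 sample as on-treatment, which fits the analysis by treatment period in SAP 6.1.

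**What to change.** In SAP 7.8.2:

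1. Add a shift table by reference range from baseline to the worst on-treatment value per subject and treatment, including unscheduled repeats. For CRP, ESR, AST, ALT and bilirubin the worst value is the highest.
2. Keep the last-value table as a second display, since it shows recovery.
3. Add a by-treatment count of subjects meeting the CRP and ESR limits as they already stand in protocol 3.3.4.1 item 7, with the second-sample confirmation. A separate liver count would largely repeat the AESI table.
4. State which samples count as on-treatment for laboratory data, in particular the period 2 admission sample, the EOT sample and follow-up retests.

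All of this uses data already collected and changes no clinical rule. The cost is SAP wording and one or two extra tables. A worst-value table will also show a few more isolated out-of-range values, in both treatments, so it should be read against the placebo column.
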